## 12.5. Appendix 5: Genetic Research

### Genetic Research Objectives and Analyses

The objectives of the genetic research are to investigate a relationship between genetic variants and:

- Response to medicine, including CAB + RPV or any concomitant medicines;
- HIV-1 susceptibility, severity and progression and related conditions.

Genetic data may be generated while the study is underway or following completion of the study. Genetic evaluations may include focused candidate gene approaches and/or examination of a large number of genetic variants throughout the genome (whole genome analyses). Genetic analyses will utilize data collected in the study and will be limited to understanding the objectives highlighted above. Analyses may be performed using data from multiple clinical studies to investigate these research objectives.

Appropriate descriptive and/or statistical analysis methods will be used. A detailed description of any planned analyses will be documented in a RAP prior to initiation of the analysis. Planned analyses and results of genetic investigations will be reported either as part of the clinical RAP and study report, or in a separate genetics RAP and report, as appropriate.

### Study Population

Any participant who is enrolled in the clinical study can participate in genetic research. Any participant who has received an allogeneic bone marrow transplant must be excluded from genetic research.

### Study Assessments and Procedures

A key component of successful genetic research is the collection of samples during clinical studies. Collection of samples, even when no a priori hypothesis has been identified, may enable future genetic analyses to be conducted to help understand variability in disease and medicine response.

- A 6 mL blood sample will be taken for deoxyribonucleic acid (DNA) extraction. A blood sample is collected at the baseline visit, after the participant has been randomized and provided informed consent for genetic research. Instructions for collection and shipping of the genetic sample are described in the laboratory manual. The DNA from the blood sample may undergo quality control analyses to confirm the integrity of the sample. If there are concerns regarding the quality of the sample, then the sample may be destroyed. The blood sample is taken on a single occasion unless a duplicate sample is required due to an inability to utilize the original sample.

The genetic sample is labelled (or “coded”) with the same study specific number used to label other samples and data in the study. This number can be traced or linked back to

the participant by the investigator or site staff. Coded samples do not carry personal identifiers (such as name or social security number).

Samples will be stored securely and may be kept for up to 15 years after the last participant completes the study, or GSK may destroy the samples sooner. GSK or those working with GSK (for example, other researchers) will only use samples collected from the study for the purpose stated in this protocol and in the informed consent form. Samples may be used as part of the development of a companion diagnostic to support the GSK medicinal product.

Participants can request their sample to be destroyed at any time.

### **Informed Consent**

Participants who do not wish to participate in the genetic research may still participate in the study. Genetic informed consent must be obtained prior to any blood being taken.

### **Participant Withdrawal from Study**

If a participant who has consented to participate in genetic research withdraws from the clinical study for any reason other than being lost to follow-up, the participant will be given a choice of one of the following options concerning the genetic sample, if already collected:

- Continue to participate in the genetic research in which case the genetic DNA sample is retained
- Discontinue participation in the genetic research and destroy the genetic DNA sample.

If a participant withdraws consent for genetic research or requests sample destruction for any reason, the investigator must complete the appropriate documentation to request sample destruction within the timeframe specified by ViiV/GSK and maintain the documentation in the site study records.

Genotype data may be generated during the study or after completion of the study and may be analyzed during the study or stored for future analysis.

- If a participant withdraws consent for genetic research and genotype data has not been analyzed, it will not be analyzed or used for future research.
- Genetic data that has been analyzed at the time of withdrawn consent will continue to be stored and used, as appropriate.

### **Screen and Baseline Failures**

If a sample for genetic research has been collected and it is determined that the participant does not meet the entry criteria for participation in the study, then the investigator should instruct the participant that their genetic sample will be destroyed. No forms are required to complete this process as it will be completed as part of the consent

and sample reconciliation process. In this instance a sample destruction form will not be available to include in the site files.

### **Provision of Study Results and Confidentiality of Participant's Genetic Data**

ViiV/GSK may summarize the genetic research results in the CSR, or separately, and may publish the results in scientific journals.

ViiV/GSK may share genetic research data with other scientists to further scientific understanding in alignment with the informed consent. GSK does not inform the participant, family members, insurers, or employers of individual genotyping results that are not known to be relevant to the participant's medical care at the time of the study, unless required by law. This is due to the fact that the information generated from genetic studies is generally preliminary in nature, and therefore the significance and scientific validity of the results are undetermined. Further, data generated in a research laboratory may not meet regulatory requirements for inclusion in clinical care.

## 12.6. Appendix 6: Definition of and Procedures for Recording, Evaluating, Follow-Up and Reporting of Adverse Events

### 12.6.1. Definition of Adverse Events

#### Adverse Event Definition:

- An AE is any untoward medical occurrence in a patient or clinical investigation participant, temporally associated with the use of a medicinal product, whether or not considered related to the medicinal product.
- NOTE: An AE can therefore be any unfavorable and unintended sign (including an abnormal laboratory finding), symptom, or disease (new or exacerbated) temporally associated with the use of a medicinal product.

#### Events meeting AE definition include:

- Any abnormal laboratory test results (hematology, clinical chemistry, or urinalysis) or other safety assessments (e.g., ECGs, radiological scans, vital signs measurements), including those that worsen from baseline, and felt to be clinically significant in the medical and scientific judgement of the investigator.
- Exacerbation of a chronic or intermittent pre-existing condition including either an increase in frequency and/or intensity of the condition.
- New conditions detected or diagnosed after study treatment administration even though it may have been present prior to the start of the study.
- Signs, symptoms, or the clinical sequelae of a suspected interaction.
- Signs, symptoms, or the clinical sequelae of a suspected overdose of either study treatment or a concomitant medication (overdose per se will not be reported as an AE/SAE unless this is an intentional overdose taken with possible suicidal/self-harming intent. This should be reported regardless of sequelae).
- "Lack of efficacy" or "failure of expected pharmacological action" per se will not be reported as an AE or SAE. However, the signs and symptoms and/or clinical sequelae resulting from lack of efficacy will be reported if they fulfil the definition of an AE or SAE.

**Events NOT meeting definition of an AE include:**

- Any clinically significant abnormal laboratory findings or other abnormal safety assessments which are associated with the underlying disease, unless judged by the investigator to be more severe than expected for the participant's condition.
- The disease/disorder being studied or expected progression, signs, or symptoms of the disease/disorder being studied, unless more severe than expected for the participant's condition.
- Medical or surgical procedure (e.g., endoscopy, appendectomy): the condition that leads to the procedure is an AE.
- Situations where an untoward medical occurrence did not occur (social and/or convenience admission to a hospital).
- Anticipated day-to-day fluctuations of pre-existing disease(s) or condition(s) present or detected at the start of the study that do not worsen.

**12.6.2. Definition of Serious Adverse Events**

If an event is not an AE per definition above, then it cannot be an SAE even if serious conditions are met (e.g., hospitalization for signs/symptoms of the disease under study, death due to progression of disease, etc).

**Serious Adverse Event (SAE) is defined as any untoward medical occurrence that, at any dose:**

**Results in death****Is life-threatening**

NOTE:

The term 'life-threatening' in the definition of 'serious' refers to an event in which the participant was at risk of death at the time of the event. It does not refer to an event, which hypothetically might have caused death, if it were more severe.

**Requires hospitalization or prolongation of existing hospitalization**

NOTE:

- In general, hospitalization signifies that the participant has been detained (usually involving at least an overnight stay) at the hospital or emergency ward for observation and/or treatment that would not have been appropriate in the physician's office or out-patient setting. Complications that occur during hospitalization are AEs. If a complication prolongs hospitalization or fulfills any other serious criteria, the event is serious. When in doubt as to whether "hospitalization" occurred or was necessary, the AE should be considered serious.

 
Hospitalization for elective treatment of a pre-existing condition that did not worsen from baseline is not considered an AE.
 

Results in disability/incapacity
 
NOTE:
 
 
The term disability means a substantial disruption of a person's ability to conduct normal life functions.
 
This definition is not intended to include experiences of relatively minor medical significance such as uncomplicated headache, nausea, vomiting, diarrhea, influenza, and accidental trauma (e.g. sprained ankle) which may interfere or prevent everyday life functions but do not constitute a substantial disruption
 

Is a congenital anomaly/birth defect

Other situations:
 
 
Medical or scientific judgment should be exercised in deciding whether reporting is appropriate in other situations, such as important medical events that may not be immediately life-threatening or result in death or hospitalization but may jeopardize the participant or may require medical or surgical intervention to prevent one of the other outcomes listed in the above definition. These should also be considered serious.
 
Examples of such events are invasive or malignant cancers, intensive treatment in an emergency room or at home for allergic bronchospasm, blood dyscrasias or convulsions that do not result in hospitalization, or development of drug dependency or drug abuse
 


Is associated with liver injury and impaired liver function defined as:
 
 
ALT <math>\geq</math> 3xULN and total bilirubin* <math>\geq</math> 2xULN (>35% direct), or
 
ALT <math>\geq</math> 3xULN and INR** <math>></math> 1.5.
 
 
* Serum bilirubin fractionation should be performed if testing is available; if unavailable, measure urinary bilirubin via dipstick. If fractionation is unavailable and ALT <math>\geq</math> 3xULN and total bilirubin <math>\geq</math> 2xULN, then the event is still to be reported as an SAE.
 
** INR testing not required per protocol and the threshold value does not apply to participants receiving anticoagulants. If INR measurement is obtained, the value is to be recorded on the SAE form.

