#### 5.5.1.1. Liver Chemistry Stopping Criteria, Participant Management and Follow-Up

Participants who develop ALT  $\geq 5$ xULN must be followed weekly until resolution or stabilization (ALT  $< 5$ xULN on 2 consecutive evaluations).

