##### When any of the liver chemistry stopping criteria is met, do the following:

- Immediately hold IP. If on LA therapy, **do not** administer another injection until approval is received from the ViiV Safety and Labelling Committee.
- Report the event to the Medical Monitor within 24 hours of learning its occurrence (Section 7.4.3.4).
- Complete the liver event eCRF and SAE eCRF, where applicable, (see Section 7.4.3.4)
- Complete the liver imaging and/or liver biopsy eCRFs if these tests are performed.
- Perform liver event follow up assessments (described below), and monitor the participant until liver chemistries resolve, stabilize, or return to Baseline values as described below.
- Make every reasonable attempt to have participants return to clinic within 24 hours for repeat liver chemistries, liver event follow up assessments (see below), and close monitoring.
- A specialist or hepatology consultation is recommended.
- Monitor participants twice weekly until liver chemistries (ALT, AST, alkaline phosphatase, bilirubin) resolve, stabilize or return to within Baseline values.

Make every attempt to carry out the **liver event follow up assessments** described below:

Viral hepatitis serology including:

- Hepatitis A immunoglobulin M (IgM) antibody;
- Hepatitis B surface antigen (HBsAg) and Hepatitis B Core Antibody (IgM);

- Hepatitis C RNA;
- Hepatitis E IgM antibody;
- Cytomegalovirus IgM antibody;
- Epstein-Barr viral capsid antigen IgM antibody (or if unavailable, obtain heterophile antibody or monospot testing);
- Syphilis screening;
- Drugs of abuse screen including alcohol;
- Serum acetaminophen test (APAP adduct test). The site must contact GSK when this test is required. Please refer to the central laboratory manual.
- Blood sample for pharmacokinetic (PK) analysis, obtained within 60 hours of last dose. Record the date/time of the PK blood sample draw and the date/time of the last dose of investigational product prior to blood sample draw on the eCRF. If the date or time of the last dose is unclear, provide the participant's best approximation. If the date/time of the last dose cannot be approximated OR a PK sample cannot be collected in the time period indicated above, do not obtain a PK sample. Instructions for sample handling and shipping are in the SPM.
- Serum creatine phosphokinase (CPK) and lactate dehydrogenase (LDH);
- Fractionated bilirubin, if total bilirubin is greater than 1.5xULN;

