- v. With the exception of the NRS questionnaire, all Patient Report Questionnaires/Surveys are recommended to be administered via validated electronic site pad or paper instrument at the beginning of the visit before any other assessments are conducted and prior to administration of the eC-CSSRS. NRS is to be given post injection. Conduct questionnaires/surveys at Withdrawal if occurring prior to Week 96.
- w. HIV TSQ (c) to be administered at Week 48 to LA injection arm only
- x. "Reason for switch" will be administered prior to randomization at Day 1. At Week 52, "Reason for Switch" will be given only to participants randomized to the "Current ART" arm.
- y. "Preference" question to be administered at Week 48 to patients randomized to CAB LA + RPV LA arm, and at Week 96 to patients randomized to the "current ART arm" who switched to CAB LA + RPV LA at the end of maintenance phase.
- z. NRS will be administered on injection visits approximately 30-60 minutes following injections. Participant should record the maximum level of pain experienced with the most recent injections.

Note: BP – Blood pressure, HR – Heart Rate, HDL – High Density Lipoprotein, LDL – Low Density Lipoprotein, PT Prothrombin Time, PTT Partial Thromboplastin Time, INR International normalized ratio

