#### **7.4.2. Laboratory Assessments**

All protocol required laboratory assessments, as defined in the Time and Events Schedule (see Section 7.1), must be performed by the central laboratory. Laboratory assessments must be conducted in accordance with the Central Laboratory Manual and Protocol Time and Events Schedule. Laboratory requisition forms must be completed and samples must be clearly labeled with the participant number, protocol number, site/centre number, and visit date. Details for the preparation and shipment of samples will be provided by the central laboratory. Reference ranges for all safety parameters will be provided to the site by the central laboratory.

If additional non-protocol specified laboratory assessments are performed at the institution's local laboratory and result in a change in subject management or are considered clinically significant by the investigator (e.g., SAE or AE or dose modification) the results must be recorded in the eCRF. Local laboratory services may be used to verify pending laboratory parameters only after consultation and agreement with the study team.

Refer to the lab manual for appropriate processing and handling of samples to avoid duplicate and/or additional blood draws.

Labs will be automatically graded by the central lab according to the DAIDS toxicity scales (See Section 12.2 "Division of AIDS Table for Grading the Severity of Adult and Pediatric Adverse Events").

For fasting laboratory assessments, an overnight fast is preferred; however, a minimum of a 6 hour fast is acceptable.

Table 6 includes lab parameters to be assessed as per the Time and Events Schedule (see Section 7.1):

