**Table 6 Safety Laboratory Assessments**

Hematology			
Platelet count	Automated WBC differential:		
RBC count	Neutrophils		
WBC count (absolute)	Lymphocytes		
Hemoglobin	Monocytes		
Hematocrit	Eosinophils		
MCV	Basophils		
Clinical Chemistry			
BUN	Potassium	AST	Total bilirubin a
Creatinine	Chloride	ALT	Albumin
Glucose c	Total CO 2	Alkaline phosphatase	Creatine phosphokinase
Sodium	Lipase	Phosphate	Creatinine clearance b
Fasting Lipid Paneld			
Total cholesterol			
HDL cholesterol			
LDL cholesterol			
Triglycerides			
Other Tests			
Plasma HIV-1 RNA e			
CD4+ and CD8+ cell counts [CD4/CD8 ratio] f			
Peripheral Blood Mononuclear Cells (PBMCs): Day 1, Week 96, Withdrawal only			
Hepatitis B (HBsAg), anti-HBc, anti-HBsAg, and hepatitis C antibody (Screening) g			
Rapid Plasma Reagin (RPR) (Screening and Baseline)			
HLA-B*5701 (Screening only)			
Prothrombin Time (PT)/International Normalized Ratio (INR)/ Partial Thromboplastin Time (PTT)			
Pregnancy test for women of childbearing potential h			
Urinalysis, urine albumin/creatinine ratio, and urine protein/creatinine ratio, urine phosphate			
Genetics Sample			
Renal biomarkers including Cystatin-C (blood), Retinol Binding Protein (RBP, blood/urine) i			
Bone biomarkers including: Bone-specific alkaline phosphatase, procollagen type 1 N-propeptide, type 1 collagen cross-linked C-telopeptide, osteocalcin, 25 hydroxy-Vitamin D i			
Follicle stimulating hormone (FSH) and estradiol (only for instances when postmenopausal status is questionable)			

MCV = mean corpuscular volume, RBC = red blood cells, WBC = white blood cells, BUN = Blood urea nitrogen, AST=aspartate aminotransferase, ALT = alanine aminotransferase, CO2 = carbon dioxide, HDL = high density lipoprotein, LDL = low density lipoprotein, HBsAg= hepatitis B virus surface antigen, PT/INR = prothrombin time/international normalized ratio.

- Direct bilirubin will be reflexively performed for all total bilirubin values  $>1.5 \times$  ULN.
- Glomerular filtration rate (GFR) will be estimated by the central laboratory using the Chronic Kidney Disease Epidemiology Collaboration (CKD-EPI) [Levey, 2009].
- For fasting glucose assessments, an overnight fast is preferred; however, a minimum of a 6-hour fast is acceptable for participants with afternoon appointments.

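### The liver SAE definition uses INR >1.5 while its footnote says INR is not required, and no liver-event, rechallenge or restart instruction orders PT/INR

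*Protocol*

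**What the plan says.** Section 12.6.2 (Appendix 6) gives two alternative laboratory definitions of a liver SAE: ALT ≥3xULN with total bilirubin ≥2xULN (more than 35% direct), or ALT ≥3xULN with INR >1.5. The INR footnote reads "INR testing not required per protocol and the threshold value does not apply to participants receiving anticoagulants" and continues "If INR measurement is obtained, the value is to be recorded on the SAE form". The bilirubin footnote beside it covers missing data: if fractionation is unavailable and both thresholds are met, "then the event is still to be reported as an SAE".

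Section 7.4.2 says "Table 6 includes lab parameters to be assessed as per the Time and Events Schedule", and Table 6 lists PT/INR/PTT under other tests. The notes to the Time and Events Table (Section 7.1) expand the abbreviations: "PT Prothrombin Time, PTT Partial Thromboplastin Time, INR International normalized ratio".

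Under Section 5.5.1.1, participants with ALT ≥5xULN "must be followed weekly until resolution or stabilization". Once a stopping criterion is met, sites are told: "Make every reasonable attempt to have participants return to clinic within 24 hours for repeat liver chemistries". They then carry out a listed work-up and monitor twice weekly. Sections 5.5.1.3.1 and 5.5.1.3.2 and Appendix 3 (PI Actions) set follow-up draws after rechallenge (twice weekly) and restart (once weekly).

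Appendix 3 also uses INR for decisions. The rechallenge checklist (Table 14) asks whether INR is currently above 1.5. The Medical Monitor and safety physician actions class a rechallenge with INR ≥1.5 as a severe reaction, and severe reactions after rechallenge or restart must be reported immediately to line management, including the committee chair.

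**The concern.** A protocol that defines a serious event by a laboratory value should either order that test when the event is suspected or say what to do when the value is absent. Here a site reading Appendix 6 is told that the test is not required, while Table 6 lists it as a scheduled safety test. A site following the liver-event instructions is never prompted to draw it.

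Two assessments depend on INR. When ALT is ≥3xULN and bilirubin stays below 2xULN, INR is the only remaining laboratory route to the liver SAE definition. After rechallenge, INR ≥1.5 is one of the triggers for immediate escalation.

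The setting matters. The risk table in Section 4.8.1 names drug-induced liver injury as a potential risk of cabotegravir, and it states that residual drug can persist for more than a year in some participants after long-acting injections stop.

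**Working it through.** No formula applies. The check sets the texts side by side.

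**1. Footnote against Table 6.** Section 7.4.2 treats laboratory tests defined in the Time and Events Schedule as protocol-required and says the Table 6 parameters follow that schedule. Table 6 restricts some tests by visit (HLA-B\*5701 to screening, RPR to screening and baseline) but puts no such limit on PT/INR/PTT. The Section 7.1 notes expand INR, which points to a row in the schedule. On its face, INR is therefore required at some visit, and the footnote says it is not. Two limits apply: the PT/INR row is not legible in this copy, so its frequency is unknown, and the footnote sits on an event definition, so it may be meant for the event only.

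**2. Event-triggered liver instructions.**

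| Instruction | What is ordered | PT/INR |
|---|---|---|
| 5.5.1.1, ALT ≥5xULN | weekly follow-up | not named |
| 5.5.1.1, stopping criterion met | repeat liver chemistries within 24 hours | not named |
| 5.5.1.1, work-up | 12 laboratory items from viral serology to fractionated bilirubin, plus blood count and autoantibodies/IgG: 12 + 2 = 14 | 0 of 14 |
| 5.5.1.1, twice weekly | ALT, AST, alkaline phosphatase, bilirubin | 0 of 4 |
| 5.5.1.3.1, rechallenge | liver chemistry tests twice weekly | not named |
| 5.5.1.3.2, restart (repeated under 7.4.4.6) | liver chemistry tests once weekly | not named |
| Appendix 3, PI Actions | liver chemistries at the same frequencies | not named |

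None of the seven names PT/INR. They are not seven independent gaps: four sit in one section, and the last restates the two above it.

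**3. Where INR is needed.** It appears in the SAE definition (Section 12.6.2), the rechallenge checklist (Table 14) and the escalation rule after rechallenge or restart (Appendix 3). None of these orders the test.

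**4. Handling of a missing value.** The bilirubin footnote gives a fallback (urine dipstick) and a default (report as an SAE). The INR footnote gives neither; it covers only a value that happens to exist.

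**5. Notification.** Table 7, as printed, has four liver rows and none mentions INR. Its first row includes ALT ≥3xULN on its own, reported within 24 hours on the SAE tool, and a table note requires sponsor contact at onset. A missing INR therefore does not delay the first report.

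**6. Dosing.** None of the stopping criteria in Section 5.5.1 uses INR, so its absence changes no stopping decision.

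**7. Cut-off.** It is written ≥1.5 in two places (the Appendix 3 rechallenge background and the escalation rule) and >1.5 in three (the Appendix 3 decision process, Table 14 and Section 12.6.2). These differ only at exactly 1.5.

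**The case against.** The strongest defence is that the INR limb is deliberately opportunistic: the footnote says the test is not mandated and asks for any value obtained to be recorded. Read as a statement about the event only, the footnote does not contradict Table 6, and the conflict becomes one of wording. That reading is plausible and cannot be excluded without the visit row. It explains the footnote but leaves the work-up, the rechallenge draws and the escalation rule without the test they rely on.

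Other safeguards narrow the gap. Participants with ALT ≥3xULN must consult the Medical Monitor before starting or continuing injections (Section 7.4.3.10). The sponsor may request supplementary tests (Section 12.6.5), and medical judgement can make any event serious (Section 12.6.2). Cases meeting stopping criteria go to adjudication with uniform data sets (Section 5.5.1.2) and to a committee with an external hepatologist (Section 7.4.4.1), and hepatology consultation is recommended. The adjudication charter is not shown and may ask for INR. These provisions permit an INR; in the text at hand none orders one.

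A reader might infer that serious liver events would go unreported. Table 7, as printed, does not support that, because ALT ≥3xULN alone already reaches the sponsor within 24 hours.

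A reader might also infer that PT/INR could simply be added to a repeat draw at ALT ≥3xULN. No general repeat draw exists at that level: weekly follow-up starts at 5xULN, and the 24-hour repeat needs a stopping criterion. For isolated ALT of 3 to <5xULN, a mandate would create a new visit.

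**Conclusion.** The point stands as minor. The footnote conflicts on its face with Table 6, subject to the unreadable visit row and the possible event-only meaning. Independently of that, the liver-event work-up and monitoring and the rechallenge and restart follow-up omit PT/INR, although the protocol's own definition, checklist and escalation rule use it. Those criteria can be assessed only if a scheduled draw coincides or someone chooses to test.

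The effect is confined to classification against the SAE definition, severity assessment and post-rechallenge escalation. First notification, dosing, the primary endpoint and power are untouched. The number of participants affected cannot be derived, because the protocol gives no rate for ALT ≥3xULN and the PT/INR visit row cannot be read. It would go too far to say that INR is never measured: a scheduled draw may coincide with an ALT rise. The difference between ≥1.5 and >1.5 is editorial only.

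**What to change.** 1. Reword the Section 12.6.2 footnote so that it no longer says INR is not required per protocol. Keep the anticoagulant exception and the instruction to record the value.
2. Add PT/INR to the liver event follow-up assessments in Section 5.5.1.1. The weekly samples ordered in the same section from ALT 5xULN can carry it too.
3. Add PT/INR to the liver chemistry draws after rechallenge or restart (Sections 5.5.1.3.1 and 5.5.1.3.2, the repeated restart text under 7.4.4.6, and Appendix 3 PI Actions).
4. Do not mandate a new draw for isolated ALT of 3 to <5xULN. If a repeat sample is taken after Medical Monitor consultation, include PT/INR.
5. As a tidy-up, use one INR cut-off in Appendices 3 and 6.

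The cost is a wording amendment and one coagulation tube at draws already ordered, using an assay already listed in Table 6. What remains is that isolated ALT of 3 to <5xULN without a repeat sample would still be classified without an INR unless a scheduled draw coincides. That is a reasonable price for not adding a visit.
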